10.1.5 Committees Structure

Not applicable

10.1.5.1 Dissemination of Clinical Study Data

This study will be registered on ClinicalTrials.gov. Release of applicable clinical study results will proceed in compliance with local regulations in accordance with the principles of Good Publication Practice.

A CSR will be prepared following completion of the study. An investigator signatory may be identified for the approval of the report if required by applicable regulatory requirements.

10.1.6 Data Quality Assurance

- All participant data relating to the study will be recorded on printed or electronic CRFs unless transmitted to the sponsor or designee electronically (eg, laboratory data). The investigator is responsible for verifying that data entries are accurate and correct by physically or electronically signing the CRF.
- Guidance on completion of CRFs will be provided in the data entry guidelines.
- The investigator must permit study-related monitoring, audits, IRB/IEC review, and regulatory agency inspections and provide direct access to source data documents.

Confidential 52 of 64

- Investigator Site Audits include, but are not limited to, review of drug supply, presence of required documents, the informed consent process, comparison of CRFs with source documents, and any other study-specific information/documentation that the auditor deems appropriate for review during the audit. The investigator agrees to participate with audits conducted at a reasonable time in a reasonable manner. Full consultation with the investigator will be made prior to and during such an audit, which will be conducted according to Indivior's or a CRO's Quality Assurance SOPs.
- In addition, this study is subject to inspections by regulatory authorities. If such a regulatory inspection occurs, the investigator agrees to allow the regulatory inspector direct access to all relevant study documents. The investigator must contact Indivior immediately if this occurs and must fully cooperate with the inspection conducted at a reasonable time in a reasonable manner.
- Monitoring details describing strategy including definition of study critical data items and
 processes (eg, risk-based initiatives in operations and quality such as risk management and
 mitigation strategies and analytical risk-based monitoring), methods, responsibilities and
 requirements, including handling of noncompliance issues and monitoring techniques
 (central, remote, or on-site monitoring) are provided in the monitoring plan.
- The sponsor or designee is responsible for the data management of this study including quality checking of the data.
- The sponsor assumes accountability for actions delegated to other individuals (eg, contract research organisations).
- Records and documents, including signed ICFs, pertaining to the conduct of this study must be retained by the investigator as dictated by ICH/GCP guidelines, as well as in accordance with the site's SOP requirements and local regulations or institutional policies. No records may be destroyed without the written approval of the sponsor. No records may be transferred to another location or party without written notification to the sponsor.

10.1.7 Source Documents

- Source documents provide evidence for the existence of the participant and substantiate the integrity of the data collected. Source documents are filed at the investigator's site.
- The investigator is responsible for the quality of the data recorded in the CRFs. The data recorded should be a complete and accurate account of the participant's record collected during the study.
- Data reported on the CRF or entered in the eCRF that are transcribed from source documents must be consistent with the source documents or the discrepancies must be explained. The investigator may need to request previous medical records or transfer records, depending on the study. Also, current medical records must be available.
- Source documents may be electronic, hard copy, or a combination of both and are defined
 as the results of original observations and activities of a clinical investigation. Source
 documents will include, but are not limited to, progress notes, electronic data, screening
 logs, and recorded data from automated instruments. All source documents pertaining to

Confidential 53 of 64

this study will be maintained by the investigator and made available for direct inspection by the authorised study personnel outlined in the ICF.

- The investigator must maintain accurate documentation (source data) that supports the information entered in the CRF.
- The sponsor or designee will perform monitoring to confirm that data entered into the CRF by authorised site personnel are accurate, complete, and verifiable from source documents; that the safety and rights of participants are being protected; and that the study is being conducted in accordance with the currently approved protocol and any other study agreements, ICH GCP, and all applicable regulatory requirements.

10.1.8 Study and Site Start and Closure

Study/Site Termination

The sponsor or designee reserves the right to close the study site or terminate the study at any time for any reason at the sole discretion of the sponsor. Study sites will be closed upon study completion. A study site is considered closed when all required documents and study supplies have been collected and a study-site closure visit has been performed.

The investigator may initiate study-site closure at any time, provided there is reasonable cause and sufficient notice is given in advance of the intended termination.

Reasons for the early closure of a study site by the sponsor or investigator may include but are not limited to the following:

For study termination:

• Discontinuation of further study drug development

For site termination:

- Failure of the investigator to comply with the protocol, the requirements of the IRB/IEC or local health authorities, the sponsor's procedures, or GCP guidelines
- Inadequate or no recruitment (evaluated after a reasonable amount of time) of participants by the investigator
- Total number of participants included earlier than expected

If the study is prematurely terminated or suspended, the sponsor shall promptly inform the investigators, the IECs/IRBs, the regulatory authorities, and any contract research organisation(s) used in the study of the reason for termination or suspension, as specified by the applicable regulatory requirements. The investigator shall promptly inform the participant and should assure appropriate participant therapy and/or follow-up.

Should this be necessary, Indivior, or a specified designee will inform the appropriate regulatory authorities of the termination of the study and the reasons for its termination, and the investigator will inform the IRB/IEC of the same. In terminating the study, Indivior and the investigator will assure that adequate consideration is given to the protection of the participants' interests.

Confidential 54 of 64

SUBLOCADE® (buprenorphine extended-release) injection Clinical Study Protocol: INDV-6000-405

10.1.9 Publication Policy

The study data will be owned by Indivior. Publication of any and all data will be at the discretion of Indivior. The investigator will not disseminate, present, or publish any of the study data without the prior written approval from Indivior to do so.

Indivior Inc.

18 Nov. 2022

- The sponsor will comply with the requirements for publication of study results. In accordance with standard editorial and ethical practice, the sponsor will generally support publication of multicentre studies only in their entirety and not as individual site data. In this case, a coordinating investigator will be designated by mutual agreement.
- Authorship will be determined by mutual agreement and in line with International Committee of Medical Journal Editors authorship requirements.

Confidential 55 of 64

10.2 Appendix 2: Clinical Laboratory Tests

- The tests detailed in Table 10 will be performed by the central laboratory.
- Protocol-specific requirements for inclusion or exclusion of participants are detailed in Section 5 of the protocol.
- Additional tests may be performed at any time during the study as determined necessary by the investigator or required by local regulations.

Table 10 Protocol-required Safety Laboratory Tests

Laboratory Assessments	Parameters		
Haematology	Platelet count		
	Red blood cell (RBC) count		
	RBC indices: • Mean corpuscular volume (MCV) • Mean corpuscular haemoglobin (MCH)		
	White blood cell (WBC) count with	Neutrophils	
	differential:	 Lymphocytes 	
		 Monocytes 	
	Eosinophils Basophils Haemoglobin Haematocrit		
Clinical Chemistry ^a	Blood urea nitrogen (BUN)	Aspartate aminotransferase (AST)	
	Albumin	Alanine aminotransferase (ALT)	
	Potassium	Alkaline phosphatase ^b (ALP)	
	Creatinine	Creatine phosphokinase (CPK)	
	Sodium	Gamma glutamyl transferase	
	Calcium	(GGT)	
	Bicarbonate	Lactate dehydrogenase (LDH)	
	Chloride	Total and direct bilirubin	
	Glucose (fasting or nonfasting)	Total protein	
Routine Urinalysis ^c	Specific gravity		
	pH, glucose, protein, blood, ketones, bilirubin, urobilinogen, n leukocyte esterase by dipstick		
	Microscopic examination (if blood or protein is abnormal) ^d		
	Appearance		
	Colour		
Pregnancy Testing	Highly sensitive urine human chorionic gonadotropin (hCG) pregnancy test (as needed for women of childbearing potential) ^c		

Confidential 56 of 64

Urine Drug Screen ^c	Opioids	
	Cocaine	
	Fentanyl ^e	
	Oxycodone	
	Opiates/Morphine	
	Amphetamines	
	Methadone	
	Cannabinoids	
	Barbiturates	
	Benzodiazepines	
	Methamphetamine	
	Phencyclidine	
Other Laboratory	Serology (HIV-1 and -2 antibodies, hepatitis B surface antigen [HbsAg],	
Tests	and hepatitis C virus antibody, PTT, and PT with INR) ^f	
NOTEC	·	

NOTES:

- ^a All events of ALT ≥3× (ULN) and bilirubin ≥2×ULN (>35% direct bilirubin) must be reported as an SAE (excluding studies of hepatic impairment or cirrhosis).
- ^b If alkaline phosphatase is elevated, consider fractionating.
- ^c On-site urine testing will be used for this protocol.
- d Microscopic examination of sediment will be performed only if the results of the urinalysis evaluation are positive (microscopic examination may include but is not limited to WBC count, RBC count, casts, and crystals).
- ^e Fentanyl may not show up in all opiate assays and should be assessed separately.
- ^f HIV-1/HIV-2, Hepatitis B and Hepatitis C antibody testing to be performed only in the absence of a positive (documented) medical history for these conditions. If there is a positive result for HIV-2/HIV-2 or Hepatitis C, an additional blood draw will be collected at the following site visit for confirmatory testing.

Investigators must document their review of each laboratory safety report.

Confidential 57 of 64

10.3 Appendix 3: Guidance on Highly Effective Contraception

Not applicable

Confidential 58 of 64

10.4 Appendix 4: Country-specific Requirements

Not applicable

Confidential 59 of 64

10.5 Appendix 5: Prohibited Concomitant Therapies

Medications prohibited during the study include, but are not limited to, the following:

Cytochrome P450 3A4 Inhibitors		Cytochrome P450 3A4 Inducers	Cytochrome P450 2C8 Inhibitors	Cytochrome P450 2C8 Inducers
Amiodarone	Ketoconazole	Barbiturates	Gemfibrozil	Rifampicin
Amprenavir	Metronidazole	Carbamazepine	Trimethoprim	
Aprepitant	Mibefradil	Dexamethasone	Glitazones	
Chloramphenicol	Miconazole	Efavirenz	Montelukast	
Cimetidine	Mifepristone	Ethosuximide	Quercetin	
Ciprofloxacin	Nefazodone	Glucocorticoids		
Clarithromycin	Nelfinavir	Glutethimide		
Clotrimazole	Nicardipine	Modafinil		
Cyclosporine	Norfloxacin	Nevirapine		
Delavirdine	Norfluoxetine	Oxcarbazepine		
Diethyl- dithiocarbamate	Propofol	Phenobarbital		
Diltiazem	Quinine	Phenytoin		
Ethinyl estradiol	Ritonavir	Pioglitazone		
Erythromycin	Saquinavir	Primidone		
Fluconazole	Sertraline	Rifabutin		
Fluoxetine	Starfruit	Rifampin		
Fluvoxamine	Telithromycin	Hypericum perforatum		
Gestodene	Troleandomycin	Sulfadimidine		
Grapefruit juice	Verapamil	Sulfinpyrazone		
Imatinib	Voriconazole	Troglitazone		
Indinavir	Zafirlukast	Troleandomycin		
Itraconazole		a/ddis/clinical-table/	124 1 1 2217	

Source: http://medicine.iupui.edu/clinpharm/ddis/clinical-table/. Accessed 31 July 2015.

Confidential 60 of 64

10.6 Appendix 6: Schedule of Assessments – Day -3 to Day 3

Table 11 Schedule of Events – Detailed Inpatient Day -3 to Day 3 With Assessment Windows

Assessment Window	Assessment		
Day -3			
Prior to vital signs and clinical laboratory assessments	12-lead ECG		
After 12-lead ECG	Vital signs		
After 12-lead ECG	Liver function assessment		
After 12-lead ECG	Urine pregnancy test		
Do	ру -2		
≤15 minutes prior to SUBOXONE dose	PK sample		
0 hour	SUBOXONE dose		
Day -1			
≤15 minutes prior to SUBOXONE dose	PK sample		
0 hour	SUBOXONE dose		
+30 minutes (±5 minutes)	PK sample		
+1 hour (±5 minutes)	PK sample		
+2 hours (±5 minutes)	PK sample		
+4 hours (±5 minutes)	PK sample		
+6 hours (±15 minutes)	PK sample		
+12 hours (±15 minutes)	PK sample		
Days 1 to 3			
Pre-Dose SUBLOCADE			
Prior to SUBLOCADE injection	Randomisation criteria reviewed and randomisation		
≤60 minutes prior to SUBLOCADE injection	Vital signs		
≤30 minutes prior to SUBLOCADE injection	PK sample		

Confidential 61 of 64

Assessment Window	Assessment		
0 hour	300 mg SUBLOCADE administration		
+1 minute (±1 minute)	Injection Site Pain VAS		
+5 minutes (±2 minutes)	Injection Site Pain VAS		
≤10 minutes	Injection site grading		
+10 minutes (±2 minutes)	Injection Site Pain VAS		
+15 minutes (±2 minutes)	Injection Site Pain VAS		
+30 minutes (±5 minutes)	Injection Site Pain VAS		
+1-hour Post-Dose SUBLOCADE			
(±5 minutes)	PK sample		
(±15 minutes)	Vital signs		
(±30 minutes)	Injection site evaluation		
+2 hours Post-Dose SUBLOCADE			
(±5 minutes)	PK sample		
(±30 minutes)	Injection site evaluation		
(±30 minutes)	Injection site grading		
+4 hours Post-Dose SUBLOCADE			
(±5 minutes)	PK sample		
+6 hours Post-Dose SUBLOCADE			
(±15 minutes)	PK sample		
+8 hours Post-Dose SUBLOCADE			
(±15 minutes)	Vital signs		
(±15 minutes)	PK sample		
+12 hours Post-Dose SUBLOCADE			
(±15 minutes)	PK sample		
+16 hours Post-Dose SUBLOCADE			
(±15 minutes)	PK sample		
+20 hours Post-Dose SUBLOCADE			
(±15 minutes)	PK sample		

Confidential 62 of 64

Assessment Window	Assessment	
+24 hours Post-Dose SUBLOCADE		
(±15 minutes)	PK sample	
(±60 minutes)	Vital signs	
+28 hours Post-Dose SUBLOCADE		
(±15 minutes)	PK sample	
+32 hours Post-Dose SUBLOCADE		
(±15 minutes)	PK sample	
+36 hours Post-Dose SUBLOCADE		
(±15 minutes)	PK sample	
+40 hours Post-Dose SUBLOCADE		
(±15 minutes)	PK sample	
+44 hours Post-Dose SUBLOCADE		
(±15 minutes)	PK sample	
+48 hours Post-Dose SUBLOCADE		
(±15 minutes)	PK sample	
(±60 minutes)	Vital signs	
Anytime during Day 3	Liver function assessment	
Discharge from Facility	Following conclusion of all assessments	

ECG=electrocardiogram; PK=pharmacokinetic; VAS=visual analogue scale

Confidential 63 of 64

STATISTICAL ANALYSIS PLAN: INDV-6000-405

Addendum

Protocol Title: A Single-Dose Study to Evaluate the Relative Bioavailability, Safety, and Tolerability of SUBLOCADE at Alternative Injection Locations in Adults

Final Version: 19 Mar 2024

NCT: NCT05704543

Statistical Analysis Plan Addendum

Protocol ID: INDV-6000-405

[REDACTED]

Date: 19MAR2024

Description:

After database lock, it was noted that the appendix of the SAP the following definition was used to derive medications prior to SUBLOCADE injection.

End Date of Non-Study Medication	Start Date of Non-Study Medication		
	Missing	< Start date of SUBOXONE	≥ Start date of SUBOXONE and ≤ end date of SUBOXONE
Missing (includes flagged as "Ongoing")	Prior Concomitant (Run-In)	Prior Concomitant (Run-In)	Concomitant (Run-In)
< Start date of SUBOXONE	Prior	Prior	Data Error
≥ Start date of SUBOXONE and ≤ end date of SUBOXONE	Prior Concomitant (Run-In)	Prior Concomitant (Run-In)	Concomitant (Run-In)

However, in the last row of this table, it implies that prior medications and Run-In concomitant medications do not include a medication started before injection and ended after last dose of SUBOXONE. The first column last row should not include the clause "and ≤ end date of SUBOXONE".

In addition, medications should be considered run-in concomitant as long as its start date is between start of SUBOXONE and SUBLOCADE injection date (if injection took place). Therefore, the last column should be split into two situations, with and without injection.

After modification, the definition should read the following:

End Date of Non-Study Medication	Start Date of Non-Study Medication			
	Missing	< Start date of SUBOXONE	≥ Start date of SUBOXONE if no injection	≥ Start date of SUBOXONE and ≤ SUBLOCADE injection date if there is SUBLOCADE injection
Missing (includes flagged as "Ongoing")	Prior Concomitant (Run-In)	Prior Concomitant (Run-In)	Concomitant (Run-In)	Concomitant (Run-In)
< Start date of SUBOXONE	Prior	Prior	Data Error	Data Error

≥ Start date of SUBOXONE	Prior Concomitant (Run-In)	Prior Concomitant (Run-In)	Concomitant (Run-In)	Concomitant (Run-In)
--------------------------	----------------------------	----------------------------	----------------------	----------------------

Implications:

Run-In concomitant medications flag and consequently, Table 14.1.5.2 will be updated.

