Participants will provide written informed consent before any protocol-related procedures commence. The study includes both a Residential (Inpatient) Period and a Non-Residential (Outpatient) Period.

Following Screening, all eligible participants must be stabilised on 12 mg SUBOXONE® (BUP/naloxone) sublingual film QD for a minimum of 7 days before the SUBLOCADE injection. Dose induction/stabilisation onto SUBOXONE may be completed as outpatient or inpatient, as necessary, according to the prescribing information for a maximum of 14 days before SUBLOCADE injection.

All participants will be admitted to the residential facility by the evening of Day -3.

The period from the first dose of SUBOXONE administered as part of this study through Day -1 will be referred to as the Run-in Period.

Following the Run-in Period, on Day 1, eligible participants will be randomised to a treatment arm.

Each treatment arm will receive a single, SC injection of 300 mg SUBLOCADE at a different injection location ie, abdomen (reference) or 1 of the alternative injection locations (test) ie, back of upper arm, buttocks, and thigh.

Safety measurements and blood samples for PK assessments during the Residential Period will be collected at scheduled time points until the participants are discharged from the residential facility on Day 3.

Participants will return to the clinical facility as outpatients for safety and PK assessments to be conducted according to the SoE until EOT.

Any participant with ongoing AEs at the EOT or ET visit will also be followed up by phone 2 weeks later for the EOS visit to assess any ongoing AEs and concomitant medications associated with those ongoing AEs only.

It is important that participants do not use any BUP-containing products, either therapeutically or illicitly during the course of the study. Such use would compromise the PK assessment of BUP and its metabolite, norbuprenorphine.

Number of Participants:

No formal statistical power analysis was performed to determine the sample size of this study. Based on historical experience from previous similar clinical trials, approximately 80 participants will be randomised in total, ideally to achieve 15 PK evaluable participants per each of the 4 treatment arms (injection locations): abdomen (reference), back of upper arm, buttocks, and thigh.

CONFIDENTIAL 12 of 64

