4 STUDY DESIGN

4.1 Overall Design

This is a multicentre, randomised, open-label, single-dose, parallel-group study in participants with moderate or severe OUD (based on criteria from the DSM-5 or documented history of moderate to severe OUD and receiving/stabilised on MOUD).

Participants will provide written informed consent before any protocol-related procedures commence within 30 days of the first SUBOXONE dose administered as part of this study (ie, after signing the ICF; see Section 10.1 [appendix] for details). The study includes both a Residential (Inpatient) Period and a Non-Residential (Outpatient) Period.

Following Screening, all eligible participants must be stabilised on 12 mg SUBOXONE (BUP/naloxone) sublingual film QD for a minimum of 7 days before the SUBLOCADE injection. Dose induction/stabilisation onto SUBOXONE may be completed as outpatient or inpatient, as necessary, according to the prescribing information for a maximum of 14 days before SUBLOCADE injection.

All participants will be admitted to the residential facility by the evening of Day -3.

The period from the first dose of SUBOXONE administered as part of this study through Day -1 will be referred to as the Run-in Period.

Following the Run-in Period, on Day 1, eligible participants will be randomised to a treatment arm.

Each treatment arm will receive a single, SC injection of 300 mg SUBLOCADE at a different injection location ie, abdomen (reference) or one of the alternative injection locations (test) ie, back of upper arm, buttocks, and thigh.

Safety measurements and blood samples for PK assessments during the Residential Period will be collected at scheduled time points until the participants are discharged from the residential facility on Day 3.

Confidential 22 of 64

Participants will return to the clinical facility as outpatients for safety and PK assessments to be conducted according to the SoE until EOT. Alternative treatment options should be discussed with the participant for initiation after EOT, including the possibility of joining another Indivior study (eg, INDV-6000-406).

Any participant with ongoing AEs at the EOT or ET visit will also be followed up by phone 2 weeks later for the EOS visit to assess any ongoing AEs and concomitant medications associated with those ongoing AEs only.

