5.3 Randomisation Criteria

- 1. Females of reproductive potential must have a negative urine pregnancy test on Day -3.
- 2. Dose-stabilised on 12 mg QD of SUBOXONE sublingual film for a minimum of 7 days (last dose on the morning of Day -1).

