9.3.5 Other Safety Analyses

TEAEs are defined as AEs with a start time that is equal to or later than the initiation of the drug treatment or any AE already present that worsens in either severity or frequency following drug exposure. Specifically, TEAEs following exposure to SUBOXONE treatment will be associated with the Run-in Period and those following SUBLOCADE treatment will be associated with the Post-randomisation Period.

TEAEs will be summarised separately for the Post-randomisation Period and the Run-in Period using safety analysis set and run-in safety analysis set, respectively. The summaries will be by injection site and overall for the Post-randomisation Period, and overall only for the Run-in Period. Complete details of the safety analyses will be provided in the SAP.

Adverse events will be coded using MedDRA and grouped by system organ class. Incidence and incidence proportion of TEAE (number and percentage of participants reporting the TEAE at least once during the Post-randomisation Period and the Run-in Period, as applicable) will be summarised by system organ class and preferred term. Separate summaries will be provided for all TEAEs, TEAEs identified as injection site reactions, serious TEAEs, drug related TEAEs, and TEAEs leading to discontinuation of study treatment.

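### Does the SAP addendum's rule for run-in concomitant medications misfile drugs started on the injection day or after a run-in failure?

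*SAP*

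**What the plan says.** The addendum was written after database lock to repair the SAP appendix rule for medications taken before the SUBLOCADE injection. The superseded last column covered start dates "≥ Start date of SUBOXONE and ≤ end date of SUBOXONE". The addendum now holds that "medications should be considered run-in concomitant as long as its start date is between start of SUBOXONE and SUBLOCADE injection date", where an injection took place, and splits that column in two:

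- Injected participants: "≥ Start date of SUBOXONE and ≤ SUBLOCADE injection date if there is SUBLOCADE injection".
- Participants not injected: "≥ Start date of SUBOXONE if no injection".

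It also removes the upper limit from the last end-date row. Its stated consequence is that the run-in flag and Table 14.1.5.2 will be updated.

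The protocol sets two boundaries that bear on this. Section 1.1 (repeated in Section 4.1) defines the Run-in Period by calendar day: "from the first dose of SUBOXONE administered as part of this study through Day -1 will be referred to as the Run-in Period". Section 9.3.5 allocates treatment-emergent adverse events by exposure: events after SUBOXONE belong to run-in, and "those following SUBLOCADE treatment will be associated with the Post-randomisation Period". Section 5.3 places the final SUBOXONE dose of randomised participants before the injection day ("last dose on the morning of Day -1"). Section 5.7 defines a run-in failure as someone dosed with SUBOXONE but not with SUBLOCADE, and gives no date on which run-in ends for that person.

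**The concern.** The injection is on Day 1 and the Run-in Period closes on Day -1, so a bound that includes the injection date reaches past the period named in the flag. Day 1 is also when injection site pain and grading are measured. An analgesic given after the injection for site pain would be flagged run-in, while the pain it treats would be a post-randomisation event. Someone reading the run-in table could take that drug as used before the injection.

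The no-injection column raises a second question. The superseded rule stopped at the end of SUBOXONE, and the new column does not stop. A drug that a run-in failure begins after leaving SUBOXONE is then labelled run-in. If it were methadone or naltrexone for opioid use disorder, which Section 6.9.1 prohibits, it could look like prohibited use during run-in.

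At stake would be the accuracy of a medication table, and through it the reading of site tolerability.

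**Working it through.** No sample size, power or error rate is involved. The check is to apply both versions of the addendum's table to test dates and set the results against the protocol.

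**Inputs.** SUBOXONE starts 14 days before the injection (the usual maximum, Section 1.1). The last dose is on Day -1 (Section 5.3). The injection is on Day 1 (Table 2). For the run-in failure rows, time is counted from the last SUBOXONE dose.

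| Participant | Medication | Superseded table | Modified table |
|---|---|---|---|
| Injected | Starts and ends within run-in | Run-in | Run-in |
| Injected | Starts in run-in, ends after last SUBOXONE dose | No matching row | Run-in |
| Injected | Starts before SUBOXONE, ends after last SUBOXONE dose | No matching row | Prior and run-in |
| Injected | Starts Day -1 | Run-in | Run-in |
| Injected | Starts Day 1 | No matching column | Run-in |
| Injected | Starts Day 2 | No matching column | Not run-in |
| Run-in failure | Starts while on SUBOXONE | Run-in | Run-in |
| Run-in failure | Starts 1, 14 or 60 days after last dose | No matching column | Run-in |

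The declared repair works: medications continuing past the last SUBOXONE dose now have a row. The two points at issue also appear. The rule includes Day 1, one calendar day after Day -1, and it has no written cap for run-in failures.

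**Which Day 1 drugs are misplaced?** That depends on the boundary used.

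| Rule | Day 1 start before injection | Day 1 start after injection |
|---|---|---|
| Protocol calendar definition (Section 1.1) | Not run-in | Not run-in |
| Protocol exposure split for adverse events (Section 9.3.5) | Run-in | Post-randomisation |
| Addendum: on or before the injection date | Run-in | Run-in |
| Alternative: strictly before the injection date | Not run-in | Not run-in |

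Against the exposure split, the addendum misplaces only drugs started after the injection on Day 1, and the strict alternative misplaces only those started before it. Separating the two needs clock times. Section 6.9 asks for start, stop and dose changes but does not say that start times are recorded.

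**How many records?** The count is (injected participants) × (share starting a drug on Day 1) × (fraction of those starting after the injection). The documents give neither of the last two. Taking all of the approximately 80 randomised as injected and assuming a 10% to 20% share:

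- all after injection: 80 × 0.10 × 1 = 8 to 80 × 0.20 × 1 = 16;
- half after injection: 80 × 0.10 × 0.5 = 4 to 80 × 0.20 × 0.5 = 8;
- none after injection: 0.

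The 10% to 20% is an assumption with no source in the documents, so the range only illustrates scale.

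**What uses the flag?** The primary analysis (Section 9.3.2.2) is an ANOVA of log AUC over 28 days and log Cmax on injection location. The secondary endpoints (Section 9.3.3) are adverse event proportions, injection site grading and the pain VAS. None is described as drawing on a medication flag. Treatment given for an adverse event is recorded with the event in the eCRF (Section 8.4), so an analgesic for site pain can still be traced to it.

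**The case for a change.** The best case for a change is that the addendum itself created the Day 1 discrepancy. The superseded start-date column stopped at the end of SUBOXONE, which for randomised participants is Day -1, and so agreed with the protocol's calendar definition. The stated aim was to derive medications before the injection, and a drug started after it is not one of them. The edit came after database lock, when boundaries should be exact, and the table was being rerun anyway. For run-in failures, a participant with adverse events ongoing at early termination is phoned two weeks later about related medications (Table 3), so a start after SUBOXONE can reach the database.

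The textual part of this stands: the flag and the defined period differ by a day, and the no-injection column has no end.

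The step to a wrong table does not. Neither Table 14.1.5.2 nor any medication data are in the documents. The addendum shows only the pre-injection rule; the main SAP's post-injection rule is not available here. Some cells carry two labels, so a Day 1 drug may also carry a post-injection label.

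For run-in failures, the exposure-based adverse event split has no end date either. Such a participant has no post-SUBLOCADE period, and capping at the last SUBOXONE dose would leave later drugs in no column of this table. Collection is also limited in practice: Section 6.9 runs it to the end-of-treatment visit, and Section 7.2 asks for a discontinuation visit if possible. Nothing in the documents connects this flag with reporting of prohibited medication.

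**Conclusion.** No change to the plan is called for. The addendum's date rule differs from the calendar definition of run-in by one day for injected participants, and it states no end for those never injected. With dates alone, assigning Day 1 is a choice of convention. Including it keeps pre-injection drugs in run-in, in line with the exposure-based adverse event split, at the price of taking in some post-injection drugs. Excluding it reverses the error. The open end for run-in failures matches how the protocol treats their adverse events and leaves no drug unclassified.

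The effect is confined to the run-in medication flag and Table 14.1.5.2. The number of affected records is unknown and may be zero. No estimate, interval or tolerability endpoint moves under either convention.

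This rests on two assumptions: that Table 14.1.5.2 is a descriptive listing or count of run-in medications, and that no other analysis in the main SAP, which is not available here, depends on the flag. A reader who knows the rule can interpret the table correctly; stating the convention there is a matter of presentation.
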